estimating equations for both the post-test score and mediators. Specifically, a path model will be estimated in which post-test scores are regressed on a dichotomous indicator of treatment, covariates described above (including pre-test scores and moderators), and on three mediators, measured as aggregate variables across the treatment period, including the quality of the classroom environment (ratio of positive to negative comments direct to the target child), consistency of teacher feedback in the classroom and home-based consequences related to school behavior. Moreover, the mediators will be simultaneously regressed on the indicator of treatment. A prototypic model is depicted below. The dashed line from covariates to post-test indicates that this actually refers to a block of variables that are omitted for presentation purposes A formal evaluation of mediation comes from

tests of whether the product of the coefficients relating treatment to mediators and mediators to outcomes (i.e., the indirect effects) differs from 0 (Bollen, 1987; MacKinnon, 2008). Whereas the joint test of the set of product terms (i.e., $a*d = b*e = c*f = 0$) provides an omnibus test of mediation, individual tests of products (i.e., $a*d = 0; b*e = 0; c*f = 0$) informs the contribution of each specific mediator. When combined with information regarding tests of indirect effects, the statistical significance

of the direct effect of treatment on post-test scores informs whether partial (i.e., if the path 't' is statistically significant) or complete (i.e., if the path 't' in the figure is not statistically significant) mediation is present. All tests of mediation will be based on the use of bootstrapped standard errors, which results in better statistical power and avoids having to make potentially unrealistic distributional assumptions about the mediated effect (MacKinnon et al., 2004; Preacher & Hayes, 2008). All mediated effects will be tested using Mplus software which includes facilities for testing individual and compound sets of mediated effects, as well as the use of bootstrapped standard errors (Muthén & Muthén, 2006).

17.2 If applicable, provide a power analysis.

NOTE: This may not apply to certain types of studies, including chart/records reviews, survey studies, or observational studies. This question is asked to elicit whether the investigator has an adequate sample size to achieve the study objectives and justify a conclusion.

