Response: We relied on our previous ($N = 63$), randomized study contrasting DRC and SAU conditions in order to compute effect sizes for the proposed study (see Preliminary Study 2). Results from that study indicated an effect size of approximately Cohen $d = .50$ (or larger) across the majority of outcomes considered. The weighted random effects effect size of between groups studies for ADHD such as this one was $.74$; thus we are using a conservative effect size relative to the larger literature ([name] et al., 2009). We also assumed that covariates (most prominently the pre-test score) would explain at least 45% of the observed variation in post-test scores (in the Goal 2 study using comparable covariates 47% of the variance for post-test scores for objective observations and teacher ratings of ADHD was explained by pre-test scores).

Given these assumptions, Aim 1 will have power of $.80$ to detect effects of Cohen $d = .50$ with $N = 71$ participants. In order to estimate power for Aim 2, we assumed treatment effects of Cohen $d = .4$ and $.6$ within moderator groups (e.g., the treatment effect would be Cohen $d = .4$ in intermediate grades compared to Cohen $d = .6$ in primary grades), which, given the sampling plan that balances participants across levels of dichotomous moderators, is consistent with the marginal treatment effect of Cohen $d = .50$ used for Aim 1. In order to detect treatment effects as small as Cohen $d = .40$ (given $R^2 = .45$, as per Aim 1) with power of $.80$, $N = 105$ participants are necessary. Hence, the total sample size needed to power Aim 2 at $.80$ is adequate at $N = 216$ (i.e., 108 participants $\times 2$ levels of moderator). Based on recent work by Fritz and MacKinnon (2007), the proposed total sample size of 216 will provide power of greater than $.80$ to detect moderate sized indirect (mediated) effects (there is no standard metric for reporting effect sizes for indirect effects). We

conclude that N=216 participants results in power of .80 or greater to address all three motivating aims. The use of modern methods for dealing with missing data (Multiple Imputation for Aims 1 and 2, Full Information Maximum Likelihood estimation for Aim 3) ensure that all N = 216 participants will contribute to each analysis.

17.3 Describe any procedures that will be used for quality control of collected data.

Response:

Treatment Integrity and Fidelity of the Consultant Activities

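### Aim 3 rests on bootstrapped standard errors; read as written, that test lacks the properties claimed for it and can lose power on specific indirect effects, so 17.1 should name the percentile bootstrap interval.

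*Combined protocol and SAP*

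**What the plan says.** Section 17.1, Aim 3, fits a path model with post-test scores regressed on treatment, covariates and "on three mediators, measured as aggregate variables across the treatment period". Mediation is judged by "tests of whether the product of the coefficients relating treatment to mediators and mediators to outcomes (i.e., the indirect effects) differs from 0". There is an omnibus test (a*d = b*e = c*f = 0) and a separate test of each product.

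On the method it says: "All tests of mediation will be based on the use of bootstrapped standard errors". The reasons given are better power and that the method "avoids having to make potentially unrealistic distributional assumptions about the mediated effect". No percentile, bias-corrected or other bootstrap interval is named in the documents.

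Section 17.1 also applies Benjamini-Hochberg adjustment throughout. Section 17.2 states that "the proposed total sample size of 216 will provide power of greater than $.80$ to detect moderate sized indirect (mediated) effects". It gives no path sizes and no test procedure, and remarks that "there is no standard metric for reporting effect sizes for indirect effects".

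**The concern.** A standard error is one number. Obtaining it by bootstrap removes a formula, but it does not remove the need for a reference distribution. If the estimated product is divided by that standard error and compared with 1.96, the normal reference is still in use. A product of two estimated coefficients is skewed unless its paths are large relative to their standard errors. The benefits that 17.1 claims come from using the bootstrap distribution itself, for example through its 2.5th and 97.5th percentiles.

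What is at stake is power for the specific mediators. Section 1.2 wants them examined individually as well as jointly, and section 10.2 expects each to mediate only part of the effect. The error of the written test is on the conservative side. It makes missed mediators more likely, not false ones, and it does not touch the Aim 1 efficacy analysis.

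**Working it through.** **Inputs.** From the documents: N = 216, 108 per group, three mediators. Assumed: two-sided .05, normal errors, no Benjamini-Hochberg adjustment, and the path sizes. Write α for the treatment-to-mediator difference between arms in SD units and β for the mediator-to-outcome path in SD units. The value α = .5 borrows the d = .50 that 17.2 uses for outcomes. Applying it to mediators is an assumption.

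**The plan's figure.** Power above .80 cannot be reproduced uniquely, because moderate is not quantified. It can only be located, as in step 3.

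**Step 1. Hand check at α = .5, β = .20 (unit residual SDs).**
- SE(α) = √(4/216) = .136, so α/SE = 3.67. SE(β) = 1/√216 = .068, so β/SE = 2.94.
- Product over its SE: 3.67 × 2.94 / √(3.67² + 2.94² + 1) = 10.80/4.81 = 2.24. Approximate power of the SE test: Φ(2.24 − 1.96) = Φ(.28) = .61.
- Requiring both paths to be significant, which tracked the percentile interval closely in simulation (.794 against .788 here): Φ(1.71) × Φ(.98) = .956 × .836 = .80.
- With α = 1.0: 7.35 × 2.94 / √(7.35² + 2.94² + 1) = 21.6/7.98 = 2.71, so Φ(.75) = .77 against 1.00 × .836 = .84. The gap narrows as α grows.

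**Step 2. Simulation, single mediator, N = 216.** Both tests use the same resamples: (i) |estimate / bootstrap SE| > 1.96; (ii) the 95% percentile interval excludes 0. Runs used 1,000 to 2,000 data sets with 500 to 1,000 resamples each. Ranges are across runs.

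| α | β | SE test | Percentile |
|---|---|---|---|
| .5 | .26 | .81–.83 | .92 |
| .5 | .20 | .60–.64 | .78–.81 |
| .4 | .20 | .43–.46 | .66–.71 |
| .5 | .15 | .36–.38 | .54–.57 |
| .8 | .20 | .82 | .85 |
| 1.0 | .20 | .82 | .85 |
| 1.0 | .15 | .57 | .60 |
| 1.5 | .20 | .81 | .83 |

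For α = .4 to .5 the gain runs from 9 points (.83 to .92) to 25 points (.46 to .71). For α of .8 or more it was about 1 to 5 points across all runs.

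**Step 3. Where power above .80 holds under the SE test.** At α = .6, β = .30 power is .97 (percentile .99). At α = .78, β = .39 both are 1.00. At α = .5, β = .25 it is .78 (percentile .90).

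**Step 4. Is the claimed power benefit there?** The SE test gave .78 against .81 for the normal-theory Sobel test at α = .5, β = .25, and .44 against .47 at α = .4, β = .20. It had no advantage.

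**Step 5. Three mediators, one specific product (residual correlation .3, α = .5).** β = .14: .26 to .43. β = .20: .54 to .72. β = .25: .73 to .87. For β = .25 with correlation 0 or .5: .76 to .89 and .63 to .80. For the sum of the three products the largest difference was .941 to .965, or 2.4 points, with power already high. The omnibus test was not simulated.

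**Step 6. Type I error.** At α = 0, β = .26 the SE test rejected in .015 to .021 of trials. The percentile interval rejected in .043 to .061. Other percentile results with one path zero were .045 to .047 (one of three mediators), .067 (α = 1.5, β = 0) and .073 (the same with a skewed mediator). The simulation SE is about .007 for the runs giving .061 to .073. With both paths zero the percentile rate was .002. The bias-corrected interval reached .065 (one mediator) and .074 to .076 (one of three).

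**The case against.** The plan never says that the estimate is divided by its standard error or compared with a normal distribution. Its stated rationale describes inference from the bootstrap distribution, so the phrase may be shorthand for bootstrap intervals. That stands, and a reader should not infer that the wrong test is certain to be run. But method and rationale disagree, the two tests can decide differently on the same data, and an unnamed interval leaves the choice open until results are seen.

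The size of the loss also depends on assumed paths. The mediators are things the intervention delivers directly. For home contingencies, section 10.2 expects most school-as-usual contacts to report none, which suggests a large treatment-to-mediator path for that mediator at least. There the gain is small. This stands too, and it is why the result is given as a range.

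A reader might go on to infer that the claim of power above .80 in 17.2 is false. The documents do not support that. The claim is for effects it calls moderate, and once α is .6 and β is .30 or more in the settings run, the SE test exceeds .80 as well.

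Finally, the percentile interval is not guaranteed to hold .05: values up to .073 were seen.

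**Conclusion.** The concern holds in a limited form. Read as written, the test in 17.1 neither avoids a distributional assumption nor improves power over the normal-theory test. Loose wording cannot be excluded. Under assumed modest paths (α = .4 to .5, β = .15 to .26, N = 216) the percentile interval gains about 9 to 25 points for a specific indirect effect. The gain falls to about 1 to 5 points when α is .8 or more, and to about 2 points at most for the summed effect. Percentile type I error is about .04 to .07 when one path is zero and the other is not small.

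The figures rest on assumed path sizes, mostly normal errors and unadjusted two-sided .05. Benjamini-Hochberg and the omnibus test were not simulated. The change is worth making because it costs almost nothing, but it concerns a mechanism aim and does not overturn the power statement in 17.2.

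**What to change.** In 17.1, Aim 3, replace the sentence on bootstrapped standard errors with wording such as: each specific indirect effect (a*d, b*e, c*f) is tested with a 95% percentile bootstrap interval from at least 5,000 resamples; its two-sided p-value is twice the smaller of the proportions of resampled products at or below 0 and at or above 0, and these p-values enter the Benjamini-Hochberg adjustment.

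Keep the omnibus test of a*d = b*e = c*f = 0. A test of the sum should not take its place, because opposing indirect effects can add to zero and the null hypothesis is different. Stating in 17.2 the path sizes behind the Aim 3 power figure would let it be checked.

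The cost is a sentence or two and a little programming to obtain the p-values, with the same resamples and no new data. With 5,000 resamples the smallest non-zero p-value is 2 × 1/5,000 = .0004, which is fine enough for the adjustment. The downside is that type I error may slightly exceed .05 in some settings, where the test as written is conservative.

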17.0 Data Management and Analysis

17.1 Describe the data analysis plan, including any statistical procedures. This section applies to both quantitative and qualitative analysis.

Response: To ensure appropriate manipulation of the independent variable the treatment integrity data described above will be collected and analyzed. The distributional characteristics of all dependent variables will be examined. If outcomes are appreciably non-normal, we will consider power transformations where appropriate. Although we expect that our cross-site and cross-cohort training efforts will mitigate the possibility of any site, cohort, or consultant differences, we will still conduct sensitivity analyses that evaluate treatment effects separately by cohort, site, and

consultant. As the study is powered for efficacy analyses and we do not anticipate being powered to detect cohort/site/consultant effects, these analyses will emphasize effect size comparisons. To the extent that any differences are revealed, we will improve cross-site and cross-cohort training and fidelity observations, as well as to consider the inclusion of site, cohort, or consultant as additional covariates. Benjamini-Hochberg adjustments will be used throughout in order to control for the false discovery rate associated with multiple comparisons across outcomes (Benjamini & Hochberg, 1995). This strategy is implemented in SAS® using PROC MULTTEST. Multiple imputation methods will be used to accommodate missing data (Allison, 2002). This strategy is implemented in SAS® using PROC MI and MIANALYZE.

Aim 1. Investigate the effectiveness of using a DRC to link the child with ADHD's IEP to daily classroom behavior.

Aim 1 will be evaluated using Analysis of Covariance (ANCOVA) models of the following form

$$y_{post} = \gamma_1 \text{pretest} + \gamma_2 \text{DRC} + \sum_{j=1}^5 \gamma_j \text{covariates} + e_i$$

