Specifically, each outcome score will be regressed on the corresponding pre-test score, a treatment indicator, and four covariates (medication status, grade level, comorbid DBD, and child gender)—the first three of which will be evaluated as potential moderators of treatment in Aim 2. Although the pretest score can be conceived as simply another covariate, it is distinguished here to emphasize the point that its inclusion results in improved statistical power relative to a repeated measures approach for evaluating treatment efficacy (Van Breukelen, 2006). Group differences on adjusted post-test scores (i.e., the significance test of γ_2) will inform the efficacy of using the DRC to enhance academic performance and behavioral outcomes beyond that associated with the routine use of IEP. Measures of primary outcome will be observations of classroom behavior and teacher ratings of academic performance. Measures of secondary outcome will include teacher ratings of symptoms and impairment related to ADHD.

Aim 2. Investigate moderators of treatment outcome.

Aim 2 will be evaluated by extending the ANCOVA model from Aim 1 as follows

$$\gamma_{post}$$

[figure not shown]
$$= \gamma_1 pretest + \gamma_2 DRC + \sum_{j=1}^2 \gamma_j covs \\ + \sum_{k=1}^3 \gamma_k moderator + \gamma_k moderator * DRC + e_i$$

Specifically, Aim 2 will extend the models estimated from Aim 1 by including three additional terms (i.e., the product of each of the three moderators—age group, comorbid DBD, IEP Quality—with the indicator of treatment). Tests of each of these three terms (i.e., $\gamma_{k1}, \gamma_{k2}, \gamma_{k3}$) will inform Aim 2. Each DRC X moderator term that is statistically significant will be probed using simple main effects (i.e., comparisons between DRC and SAU outcomes within each level of the moderator variable) in order to delineate the differential magnitude of treatment on adjusted post-test scores as a function of a given covariate (i.e., primary vs. secondary grade; ADHD only vs. ADHD+DBD; High Quality vs. Low Quality IEP).

Aim 3. Investigate mediators of treatment outcome. Aim 3 will be evaluated using a path analytic approach for testing mediation. The path model will extend the ANCOVA models above by simultaneously

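### The .80 power stated for Aim 2 belongs to a DRC vs SAU effect within one moderator level; the DRC × moderator test that the plan names has about 17% power

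*Combined protocol and SAP*

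**What the plan says.** **What is tested (17.1, Aim 2).** The ANCOVA model is extended by "the product of each of the three moderators—age group, comorbid DBD, IEP Quality—with the indicator of treatment", and the tests of these three terms inform the aim. Comparisons of DRC with SAU inside a moderator level come afterwards: "Each DRC X moderator term that is statistically significant will be probed using simple main effects". This fits the hypotheses in 1.2, each of which says that DRC will work better in one kind of child than in another.

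**What is powered (17.2).** For Aim 1, "Aim 1 will have power of $.80$ to detect effects of Cohen $d = .50$ with $N = 71$ participants", with covariates explaining 45% of the outcome variance. For Aim 2 the plan assumes d = .4 in one moderator level and .6 in the other, "given the sampling plan that balances participants across levels of dichotomous moderators". The calculation starts "In order to detect treatment effects as small as Cohen $d = .40", arrives at 105 children, carries this to 108 in each of two levels, and concludes that "the total sample size needed to power Aim 2 at $.80$ is adequate at $N = 216". The section closes by claiming that "N=216 participants results in power of .80 or greater to address all three motivating aims".

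**Multiplicity (17.1).** "Benjamini-Hochberg adjustments will be used throughout in order to control for the false discovery rate associated with multiple comparisons across outcomes". The power section does not allow for this.

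**The concern.** Detecting a treatment effect of .40 against zero in one subgroup is a different task from detecting that the effects in two subgroups differ by .20. The second has half the effect size and, at the full N = 216, twice the standard error of the overall treatment effect. The difference of .20 never enters the calculation in 17.2, and no other section powers a product term.

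Two things are at stake. First, a non-significant interaction would be read as coming from a test with 80% power, and so as fair evidence that grade, comorbid DBD or IEP quality do not alter the effect. Second, the Aim 2 step is the only worked calculation that leads to 216, since Aim 1 is said to need 71.

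**Working it through.** **Inputs from the documents.** N = 216, 108 per arm (4.1); covariate R² = .45, so residual variance is .55 in units of the outcome variance (17.2); d = .4 and .6 in the two levels of a balanced moderator (17.2); no loss, since all 216 are said to contribute (17.2).

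**Assumption.** Neither alpha nor sidedness is stated. I take two-sided .05 because it matches the plan's Aim 1 figure (step 1). Power is from the noncentral t distribution.

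**1. The plan's own figures.** For a DRC vs SAU effect in n children split 1:1, SE = √(4 × .55 / n).

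| d | n | SE | Power, two-sided .05 | Power, one-sided .05 |
|---|---|---|---|---|
| .50 | 71 | 0.176 | .80 | .88 |
| .40 | 105 | 0.145 | .78 | .86 |
| .40 | 108 | 0.143 | .79 | .87 |

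A normal approximation gives .789 at 105 and .800 at 108. So the plan's numbers reproduce closely, as the power of a treatment effect against zero.

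**2. The test that decides Aim 2.** The quantity is .6 − .4 = .2. With four cells of 54 children,

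SE = √(4 × .55/108 + 4 × .55/108) = √(16 × .55/216) = 0.202.

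The SE of the overall treatment effect is √(4 × .55/216) = 0.101, half as large. The noncentrality is .2 / 0.202 = 0.99. With 206 degrees of freedom:

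- power is 16.7% two-sided and 25.6% one-sided;
- the difference detectable with power .80 is d = 0.57 two-sided and 0.50 one-sided;
- power .80 for a difference of .2 would need about 1,730 children.

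Simulations of the full model with all three product terms agree: 15.5% (4,000 runs) and 16.2% (20,000 runs), both two-sided.

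**3. Sensitivity (two-sided unless noted).**

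| Change from step 2 | Power |
|---|---|
| R² = .47 (the pilot value in 17.2) | 17.1% |
| R² = .60 / .80 / .90 (assumed) | 21% / 37% / 64% |
| Moderator split 30:70 (assumed) | 14.8% (23.0% one-sided) |
| IEP quality as a continuous score (assumed normal, slope giving .2 between median-split halves) | 23.5% (34.2% one-sided) |
| Alpha .05/3, the strictest Benjamini-Hochberg step over three tests | 8.0% |
| Benjamini-Hochberg over an assumed 3 to 9 tests, simulated | about 4% to 11% |

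**4. Balance.** The blocks in 10.1 are formed from medication and grade only, so the balance that 17.2 relies on is designed in for grade but not for comorbid DBD or IEP quality. Section 10.2 defines IEP quality as a numeric score, while 17.1 contrasts high with low quality and gives no cut-point.

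**5. Aim 1.** At N = 216 and d = .50, power is .9985.

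**The case against.** **The plan says what it powers.** Section 17.2 states openly that it detects treatment effects as small as .40, so one can argue that within-level power was intended. But 17.1 makes within-level comparisons conditional on a significant interaction, so their power cannot stand as the power of the aim. Under the assumed pattern, within-level power is .79 at d = .4 and .99 at d = .6. Both levels would usually be significant, which by itself shows no moderation.

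**The 17% depends on a difference of .20.** This stands. At the same N, differences of .4 and .5 would have about 51% and 69% power. But .4 and .6 are the plan's own assumptions, and 1.2 gives directions without sizes.

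**The consequences are limited.** This also stands. Aim 1 carries the efficacy question, and the interaction estimates remain valid, only imprecise. What is wrong is an explicit power claim for a stated aim with directional hypotheses.

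**Some side figures rest on thin ground.** Fair. The Benjamini-Hochberg range depends on a number of tests that the plan does not give, and a larger family would lower it further. The wording of 17.1 and 17.2 leans towards a two-level IEP quality variable, so the continuous case is the less supported reading. Neither figure is needed for the conclusion.

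**The moderator list is unsettled.** In 17.1 the Aim 1 text names medication, grade and comorbid DBD as the moderators for Aim 2; the Aim 2 text names age group, comorbid DBD and IEP quality. The two should be reconciled. The power of a balanced two-level term is the same for either list.

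**Conclusion.** The concern holds. The stated .80 is the power to detect d = .40 between DRC and SAU within one moderator level. For the test that decides Aim 2, the plan's own inputs give about 17% per test, so the assumed pattern would be missed about five times in six (about three in four if one-sided). The difference that N = 216 can detect with power .80 is about d = .57, nearly three times the one assumed.

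This rests on two-sided .05, R² = .45, a balanced two-level moderator, no loss and no multiplicity adjustment. For a two-level moderator, imbalance, loss or Benjamini-Hochberg adjustment can only lower the figure. No variant examined reaches .80. Aim 1 stands, and no position is taken here on Aim 3.

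**What to change.** In 17.2, replace the Aim 2 power statement with wording such as:

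> Assuming a two-sided .05 level before Benjamini-Hochberg adjustment, N = 216, R² = .45 and a balanced two-level moderator, power to detect a DRC × moderator difference of d = .20 (.60 vs .40) is about 17% per test, and the difference detectable with power .80 is about d = .57. The blocks balance grade but not comorbid DBD or IEP quality; for a two-level moderator with unequal levels, power is lower.

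Keep 108 per level only as the power of a within-level effect, and remove Aim 2 from the closing claim about all three aims. Settle the moderator list in 17.1 so that the sentence on blocks names the right variables.

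Optionally, report each interaction with a 95% confidence interval. Its expected half-width is about 1.97 × 0.202 = 0.40 in d.

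**Cost.** A few sentences, with no change to enrolment or tests. The stated power for Aim 2 becomes less favourable, and 216 loses its only worked derivation. The plan could then justify 216 by the high power for Aim 1 and by the precision of the moderator estimates.

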The recruitment plan will aim for an equal number of subjects in the DRC and SAU groups, and participants will be block randomized across potential moderator variables including medication and grade level. In the Goal 2 study, for which these variables were unselected, 52% of the final sample was prescribed medication and 66% were in grades K-3 and 34% were in grades 4-6. Thus, it appears that the plan to have an equal number of subjects in each block is feasible with careful attention to recruiting participants in the older grades in the present application. Block randomization based on child psychoactive medication status will promote equal distribution of participants across this variable. The medication variable will be defined as “no medication” if the child is not prescribed psychoactive medication immediately prior to randomization and as “taking medication” if the child is prescribed psychoactive medication and it is being actively administered at the time of randomization. In sum, an equal number of participants (N=72/year) will be enrolled in four blocks each year (i.e., No medication/Primary grade; No medication/Intermediate grade; Taking medication/Primary grade; Taking medication/Intermediate grade). Random assignment will be conducted following the completion of all baseline measures by a blinded member of the study team ([name]). Following randomization, a form letter will be generated that informs the study staff and participating family of group

assignment. Consultants will then be randomly assigned to the case with an equal number of DRC and SAU cases assigned to each consultant.

For those students who are medicated with stimulant medication, we will ask parents to obtain permission from the child's doctor to withhold medication for the assessment days in January and May so as to collect information on the child's behavior when unmedicated.

Intervention Groups

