21.0 Risks to Subjects

21.1 List the reasonably foreseeable risks, discomforts, hazards, or inconveniences to the subjects related to their participation in the research. Consider physical, psychological, social, legal, and economic risks. Include a description of the probability, magnitude, duration, and reversibility of the risks.

NOTE: Breach of confidentiality is always a risk for identifiable subject data.

Response: **Risk:** Participants may experience mild and transitory psychological discomfort from completing research measures, including reporting on child emotional and behavior problems and academic difficulties. **Procedure:** Participants and their parents will be advised to ask questions of study personnel if confidentiality is of a concern, and to refrain from answering questions that cause them personal distress.

Risk: Participants may face risk as they may experience mild and transitory psychological discomfort from changing their behaviors as part of the study interventions. **Procedure:** The centers at FIU and at UB are quite experienced at running psychosocial intervention for youth with ADHD in school and with parents. We experience very low attrition rates (under 5% from our clinical and research programs). None the less, children and parents can refuse to continue to participate in the study at any time.

Risk: Teachers may find the additional consultation and implementation of new strategies to be burdensome. **Procedure:** We are quite experienced in teacher consultation both in IES- and NIH-funded studies and in nonresearch work in the Buffalo and Miami-Dade schools. Our groups are well known to teaching staff, given that we provide regular inservice instruction and consultation to the districts, and we have excellent rapport with principals, teachers, psychologists/social workers, and administrators. We have had very low rates of teacher refusal to participate in the studies, and we anticipate that to continue for

this project. Indeed, the vast majority of teachers find the consultations to be helpful in coordinating school-based supports for their students with ADHD. We will work with teachers to schedule consultations at times teachers identify as most convenient. Furthermore, consultations are intended to be collaborative and teachers' input is encouraged.. Efforts will be made to collaborate with and reengage teachers who refuse to contribute to any specific intervention or study activity.

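### The .80 power claimed for Aim 2 is a within-level figure that has a basis only for grade, has no margin there, and is not the power of the moderator tests

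*Combined protocol and SAP*

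**What the plan says.** Section 17.2 assumes effects of d = .4 and .6 in the two levels of a moderator and covariates that "would explain at least 45% of the observed variation in post-test scores". It gives N = 105 for power .80 at d = .40 and takes 108 children in each of two levels, 216 in all, as enough for Aim 2. It justifies the equal levels by "the sampling plan that balances participants across levels of dichotomous moderators". No allowance is made for loss, because multiple imputation and full-information maximum likelihood are said to "ensure that all N = 216 participants will contribute to each analysis". The conclusion is that the authors "conclude that N=216 participants results in power of .80 or greater to address all three motivating aims".

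Three other places bear on this:

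- Section 10.1 says participants are "block randomized across potential moderator variables including medication and grade level" and lists four blocks, formed by medication status and primary or intermediate grade.
- Section 17.1 (Aim 2) names the tested moderators as age group, comorbid DBD and IEP quality. It tests each through its product with treatment, and looks at effects within levels only after a significant product term.
- Section 21.1 reports past experience: "We experience very low attrition rates (under 5% from our clinical and research programs".

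**The concern.** The Aim 2 calculation needs each moderator to split the sample in half, but only grade is among the factors that define the blocks. DBD status comes from symptom ratings and IEP quality from a computed score (section 10.2), and nothing fixes either at 50:50. The N of 105 does not sit well with the plan's own Aim 1 figure of 71, and a claim of .80 or greater leaves no room for any lost post-test. The calculation also concerns the treatment effect inside one level, whereas section 17.1 decides Aim 2 by a difference between levels.

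A reader who takes 17.2 at face value would treat a non-significant moderator test, or a null result within a level, as coming from a study with at least .80 power to show otherwise.

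**Working it through.** **Inputs.** From 17.2: d = .50 (Aim 1), d = .40 and .60 (Aim 2), R² = .45, power .80, N = 71 and N = 105, total 216. From 4.1 and 10.1: 1:1 allocation. Alpha is not stated in the power section. I assume .05 two-sided, which agrees with the plan's 71; one-sided .05 would give 56. No false-discovery adjustment (17.1) is included.

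**Formulas.** The noncentrality for N children in 1:1 allocation is d × sqrt(N / (4 × .55)). The normal-formula size is N = 4 × .55 × (1.960 + 0.842)² / d². The t figures use the noncentral t.

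**Aim 1 first (d = .50).**

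- Normal formula: 69.1, or 70 with equal arms.
- t method: power at N = 71 is .7998, and the first N at or above .80 is 72.
- The plan's 71 therefore agrees with the t method to rounding.

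**Aim 2, within one level (d = .40).**

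- Normal formula: 107.9, so 108.
- t method: 110. Scaling the plan's own figure gives 71 × (.50/.40)² = 110.9.
- In the other direction, 105 × (.40/.50)² = 67.2, not 71.
- Power at 105: .78 (t), .79 (normal).
- Power at 108: .793 (t), .800 (normal).
- With 5% loss, 108 × .95 = 102.6 per level: .77 (t), .78 (normal).

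**Balance.** Section 10.1 enrols 72 children a year in four equal blocks, 18 each. Each grade level takes two blocks, 36 a year. With 216/72 = 3 years, that is 108 per grade level. No such count can be derived for DBD or IEP quality.

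The documents give no shares for those two, so the shares below are assumptions. The t method is used, with N = 216 and no loss.

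| Share in smaller level | n, smaller / larger | Smaller level has d = .40: power there | Smaller level has d = .60: power in smaller / larger level |
|---|---|---|---|
| 30% | 64.8 / 151.2 | .57 | .89 / .91 |
| 35% | 75.6 / 140.4 | .64 | .93 / .89 |
| 40% | 86.4 / 129.6 | .70 | .96 / .86 |
| 50% | 108 / 108 | .79 | .99 / .79 |

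Unequal levels also move the average effect away from the .50 that 17.2 ties to balance. At 30:70 it is .3 × .4 + .7 × .6 = .54, or .3 × .6 + .7 × .4 = .46.

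**The test that decides Aim 2.** The difference to detect is .6 − .4 = .20. With 108 per level its standard error is sqrt(4 × .55/108 + 4 × .55/108) = .202. The ratio is .20/.202 = 0.99, and two-sided power is about .17. Power of .80 would need a difference of 2.80 × .202 = .57, or about 16 × .55 × 2.80² / .20² ≈ 1,727 children (unrounded multiplier 2.8016).

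**The case against.** Four points can be made for the plan.

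- **The arithmetic gap is small.** The plan uses 108 per level, not 105, and the normal formula gives .800 there. Section 17.1 probes simple effects from one model on all children; with about 205 error degrees of freedom, power at 108 is .797. At the 47% explained variance seen in the pilot it is .81. This stands. A reader might infer that 105 is a serious miscalculation, but it costs one to three points of power, including 5% loss.
- **The imputation sentence is literally true.** All 216 children do enter each analysis after imputation. This stands too, so the sentence should not be called false. What it cannot support is full-sample power, because an imputed post-test does not restore the information that was lost.
- **Imbalance need not hurt.** A reader might infer that power for DBD and IEP quality is only .57 to .70. The documents do not support that. Those figures need the smaller level to carry d = .40. Section 1.2 predicts the larger effect in children with DBD and in those with low-quality IEPs. If that level is the minority at 30 to 40%, both levels exceed .80. Neither the shares nor a cut-point for IEP quality is given.
- **Within-level power is secondary.** Simple effects are examined only after a significant product term. This is correct, but it does not rescue 17.2. It means the .80 describes a follow-up comparison and not the Aim 2 test.

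**Conclusion.** The .80 power stated for Aim 2 does not follow from the plan's own inputs and design. The size of the problem differs by part.

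- **Balance:** 108 per level is supported for grade only, provided the equal-block recruitment is achieved. For DBD and IEP quality it has no basis, and neither the size nor the direction of the effect on power can be fixed from the documents.
- **Arithmetic and loss:** for grade, within-level power at d = .40 is .79 to .80 with no loss and .77 to .78 at 5% loss. The 5% is the ceiling of the teams' past experience, not a projection for this trial.
- **What is powered:** all these figures are for simple effects. For .4 versus .6, the moderator tests have about .17 power with equal levels, before any false-discovery adjustment.

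The results assume two-sided .05 and R² = .45. A reader might also infer that Aim 1 is short of children. It is not: at N = 216 and d = .50 its power is above .99 before loss and multiplicity adjustment. Nor should the grade figure of about .79 be read as showing that 216 children are nearly enough for Aim 2.

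**What to change.** Change the wording of section 17.2 as follows.

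1. Limit the statement about balanced moderator levels to grade.
2. Replace 105 with 108 (normal) or 110 (t), naming the method and alpha. Give within-level power at d = .40 with 108 per level as about .79 to .80, or .77 to .78 with 5% loss.
3. For DBD and IEP quality, give within-level power over a range of assumed level shares, and say which level carries d = .40.
4. Keep the imputation sentence, but add that including every child does not recover the information in missing post-tests.
5. Label these figures as power for simple effects. Withdraw the claim of .80 or greater for Aim 2, and report the power of the treatment-by-moderator terms: about .17 for .4 versus .6 at N = 216, or a detectable difference of about .57.

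This is a text change with no change to design or conduct. The cost is a less favourable power statement for Aim 2. The rewording does not raise the power of the moderator tests and should not be presented as showing that the sample is sufficient for them.
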